6.1.1.4 Supportive analyses

The MIHAS scores of left and right IOH at baseline and Week 8 as assessed by a blinded evaluator will be presented by summary statistics for the TN, TC, TRT and CTL groups. Furthermore, the absolute change from baseline to Week 8 will be summarized descriptively. In this instance, baseline refers to the screening visit for all groups.

Additionally, MIHAS scores (0 = none to minimal, 1 = mild, 2 = moderate, 3 = severe, 4 = extreme) of left and right IOH at baseline and Week 8 are described in frequency tables via counts (n) and percentages (%) for the same groups as for the summary statistics.

Supportive analyses will be based on observed cases in the ITT and the PP population.

[figure not shown]
6.1.2 Secondary Effectiveness Endpoints

If not otherwise specified, the analyses of secondary effectiveness endpoints will be conducted based on observed cases for the ITT and PP population for the TN, TC and TRT groups only. Subgroup analyses will be performed only based on the ITT population, using observed cases.

GAIS

FACE-Q

Subgroup analysis

Investigator and subject GAIS, as well as FACE-Q Satisfaction with Eyes Scores, will be analyzed for subgroups TN and TC, as part of the analyses described above.

[figure not shown]
In addition to the overall summary statistics defined above, summary statistics for investigator and subject GAIS and FACE-Q Satisfaction with Eyes Rasch-Transformed Scores will also be

provided for TN, TC and TRT groups, based on observed cases in the ITT population, for the following subgroups:

- Baseline MIHAS (2 vs. 3),
- Site,
- · Sex (male vs. female),
- Fitzpatrick Skin Type (I-III vs. IV-VI).

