7.2.1.2 Secondary Effectiveness Endpoints

Note: For all secondary endpoints, Week 8 corresponds to the time from last injection (either baseline or touch-up injection) for subjects randomized to treatment only (TN and TC groups).

- GAIS score at Week 8, as assessed by the treating investigator.
- GAIS score at Week 8, as assessed by the subject.
- FACE-Q[™] Satisfaction with Eyes scores and changes from baseline to Week 8, as assessed by the subject.

Note: FACE-Q evaluates both eyes concurrently.

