8.2 Discussion of Study Design, Including the Choice of Control Groups

As detailed in Section 8.1, this is a prospective, multicenter, randomized, comparative, evaluator-blinded, pivotal study designed to evaluate the effectiveness and safety of BBL for the correction of volume loss in the IOH area.

Since no approved, marketed products are currently available in the US for treatment of the IOH region, an untreated-control group will be utilized for this study. To maximize the number of subjects exposed for generation of adequate safety data, control subjects will receive delayed treatment with BBL upon completion of all Week 8 effectiveness assessments.

As subject satisfaction is the primary goal of aesthetic medicine, subjects may undergo a touch-up treatment after initial injection to achieve optimal correction. Subjects randomized to treatment will also be eligible for retreatment at 48 weeks post last injection (i.e., baseline injection or touch-up, if applicable) for further aesthetic IOH enhancement. Optional retreatment will help improve compliance with the study protocol (i.e., minimize early discontinuation) and ensure subjects will complete the study with aesthetic IOH improvement. Retreating subjects at 48 weeks post last injection will also provide additional safety data associated with repeat treatment.

Injection volumes to be administered in this study (see Section 10.5.1.2.6) represent a safe standard for IOH treatment and are consistent with volumes utilized in a Belotero Balance pilot study of IOH treatment (M930121001).

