2.2 Clinical Study Objectives

Effectiveness

Confirm the effectiveness of BBL injection for the correction of volume loss in the IOH area by demonstrating superiority to untreated control.

Safety

Confirm the safety of BBL injection for the correction of volume loss in the IOH area.

3 Determination of Sample Size

The primary effectiveness analysis considers the proportion of subjects with at least 1-point improvement on the MIHAS for both IOHs, as assessed by the blinded evaluator at Week 8 compared to baseline. For this analysis, subjects from TN and TC groups will be pooled into the Treatment Group TRT, and subjects from CDTN and CDTC groups (data before any treatment) will be pooled into the Control Group (CTL).

A two-step hierarchical-testing procedure is foreseen for the primary analysis:

- 1. Treatment Group (TRT) shows a response rate of more than 50%, and
- 2. Treatment Group (TRT) is superior to the Control Group (CTL).

This hierarchical-testing procedure will keep the overall one-sided error rate of $\alpha = 0.025$, and no adjustment for multiplicity is necessary.

Sample-size estimation was based on methods implemented for the binomial and Fisher's exact test. In this context, it should be noted that the use of two-sided 95% Wilson confidence intervals (CI) and Newcombe CIs, instead of binomial and Fisher's exact tests as referenced in the next paragraph, will deliver more efficient results (i.e. smaller CIs). The CI-based methods have the advantage that they can be used for multiple imputation of missing data. Hence, sample size calculations were based on slightly more conservative test procedures, so that the determined power will also suffice for tests based on CIs.

Sample-size estimation for test Step 1 was performed with a one-sided binomial test at an error level of 2.5% to evaluate whether the response rate was significantly larger than 50%. It was aimed to ensure a power of 90%. The binomial test will be conducted on the pooled data (TRT) from both treatment groups (TN and TC). Due to the allocation ratio of 2:2:1:1, the two treatment groups (TN and TC) will be approximately equally represented. Calculations for test Step 2 were performed with a one-sided Fisher's exact test for unequal n's, at an error level of 2.5%, to detect a statistically significant difference between a response rate in Group TRT of 70% compared to 30% in Group CTL. A power of at least 90% was assumed.

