5.1.2 Secondary Effectiveness Endpoints

Note: For all secondary endpoints, Week 8 corresponds to the time from last injection (either baseline or touch-up injection) for subjects randomized to treatment only (TN and TC groups). I.e. data from Visit 3 will be used.

- GAIS score at Week 8, as assessed by the treating investigator.
- GAIS score at Week 8, as assessed by the subject.
- FACE-QTM Satisfaction with Eyes scores and changes from baseline to Week 8, as assessed by the subject.

Note: FACE-Q evaluates both eyes concurrently.

[figure not shown]

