For subjects of treatment groups TN and TC who do not receive retreatment and for subjects of treatment groups DTN and DTC, Cycle 1 is defined as the period from initial injection until study end. Results at visit V8 and V9 for TN and TC subjects will be presented as 56 and 72 weeks post last injection (in Cycle 1), respectively.

Subjects who never received treatment do not have a cycle 1 or cycle 2.

Section 6.4.1 describes methods for handling of data collected at the end of study visit (either visit V9 for subjects in TRT or visit C7 for subjects in CDTRT) among subjects prematurely discontinuing the study.

For the primary and secondary effectiveness analyses, if not stated otherwise, "Week 8" refers to visit V3 (8 weeks post last injection in Cycle 1) for subjects in TRT, TN, and TC and visit C1-a (8 weeks post screening) for subjects in CTL.

All data will be listed. If not stated otherwise, listings will be presented based on all subjects randomized.

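### On the visible text, the secondary FACE-Q satisfaction endpoint is summarised in treated subjects only, so it is an uncontrolled before-and-after result although an untreated arm is randomized

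*SAP*

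**What the plan says.** The effectiveness objective in SAP 2.2, matched in Protocol 7.1, is: "Confirm the effectiveness of BBL injection for the correction of volume loss in the IOH area by demonstrating superiority to untreated control". Subjects are randomized 2:2:1:1, which pools to 2:1 treated to untreated.

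One of the three secondary effectiveness endpoints in SAP 5.1.2 is "FACE-QTM Satisfaction with Eyes scores and changes from baseline to Week 8, as assessed by the subject". The note above that list ties Week 8 to the time since last injection "for subjects randomized to treatment only (TN and TC groups). I.e. data from Visit 3 will be used". Protocol 7.2.1.2 carries the same restriction, "for subjects randomized to treatment only (TN and TC groups". Neither note has a qualifier.

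The analysis rules follow suit. SAP 6.1.2 says secondary analyses are "conducted based on observed cases for the ITT and PP population for the TN, TC and TRT groups only", and Protocol 13.4.1.2 has an equivalent sentence. Both sentences open by allowing for exceptions specified elsewhere. The FACE-Q subgroup summaries in SAP 6.1.2 are again for TN, TC and TRT.

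Two places point the other way. The general part of SAP section 6 defines Week 8 for primary and secondary effectiveness analyses together, and includes "visit C1-a (8 weeks post screening) for subjects in CTL". Protocol 8.2 says that "control subjects will receive delayed treatment with BBL upon completion of all Week 8 effectiveness assessments".

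**The concern.** A change from baseline within treated subjects mixes any device effect with whatever would have happened anyway: drift over time, the effect of completing the questionnaire again, regression to the mean, and being in a trial. The randomized untreated arm exists to remove that shared part. The primary MIHAS endpoint uses it, and so do the supportive MIHAS summaries in SAP 6.1.1.4. The visible rules for FACE-Q do not.

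FACE-Q differs from GAIS here. GAIS rates a post-treatment photograph against a pre-treatment one (Protocol 11.2.1.3), so a treated-only analysis is natural. A satisfaction score can be given by an untreated subject.

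What is at stake is interpretation. Protocol 6.2 already describes the pilot FACE-Q results as improvement over time after injection and lists this with the potential benefits. If the pivotal result is reported the same way, it would not address the trial's stated comparison.

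**Working it through.** **1. The plan's own figures.** The only sizing in the documents is for MIHAS.
- Step 1, exact one-sided binomial, n = 80, 50% vs 70%: 50 responders are needed (actual alpha 0.0165) and power is 94.1%. The plan says at least 94%.
- Step 2, one-sided Fisher exact, 80 vs 40, 70% vs 30%: power is 98.4%. The plan says at least 98%.
- Overall: 0.941 × 0.984 = 0.926. The plan says above 92%.
- Drop-out: 120 / (1 − 0.20) = 150.

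All of these reproduce. For FACE-Q they supply only the arm sizes: 80 vs 40 evaluable, or 100 vs 50 with no drop-out.

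**2. The passages side by side.**

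| Place | Groups named for secondary endpoints |
|---|---|
| Protocol 7.2.1.2 | TN, TC; no exception allowed |
| SAP 5.1.2 | TN, TC, Visit 3; no exception allowed |
| Protocol 13.4.1.2 | TN, TC, TRT, unless specified otherwise |
| SAP 6.1.2 | TN, TC, TRT, unless specified otherwise |
| SAP 6, Week 8 definition | V3 for TRT, TN, TC; C1-a for CTL, unless stated otherwise |

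The last row supplies a visit for CTL but assigns it no secondary analysis.

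**3. What a shared change could do.** The documents give no FACE-Q SD or expected shift, so I work in SD units of the change score and assume a range. With no device effect and a change of s SD common to both arms, the probability that a within-arm 95% CI at n = 80 lies wholly above zero is 1 − Φ(1.96 − s√80).

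| s (SD) | Probability |
|---|---|
| 0 | 2.5% |
| 0.1 | 14% |
| 0.2 | 43% |
| 0.3 | 77% |

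A between-arm comparison stays at 2.5% for change that is truly common. This illustrates the mechanism only; the visible plan contains no such within-arm test.

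**4. What a between-arm estimate would deliver.** SE = √(1/n_T + 1/n_C) in SD units; half-width = 1.96 × SE; power = Φ(d/SE − 1.96); detectable difference = (1.960 + z) × SE, with z = 0.842 for 80% power and 1.282 for 90%.

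| | 80 vs 40 | 100 vs 50 |
|---|---|---|
| SE | √0.0375 = 0.194 | √0.03 = 0.173 |
| 95% CI half-width | 0.38 | 0.34 |
| Power at 0.3 SD | 34% | 41% |
| Power at 0.5 SD | 73% | 82% |
| Power at 0.7 SD | 95% | 98% |
| Detectable, 80% power | 0.54 | 0.49 |
| Detectable, 90% power | 0.63 | 0.56 |

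**5. Timing.** Controls reach C1-a 8 weeks after screening. Treated subjects start 3 to 10 days after screening and reach V3 8 weeks after their last injection. With a touch-up at about Week 4, V3 falls 4 + 8 = 12 weeks after first injection, so those subjects are assessed about 4 weeks later than controls, plus the 3 to 10 days.

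**The case against.** The strongest reply is that the governing text cannot be read. In SAP 6.1.2 the FACE-Q heading has nothing visible beneath it, although SAP 6.4.1 says that missing FACE-Q scores are handled in that section. The sections on other effectiveness endpoints are also not visible. This stands: a reader might infer that the control arm never enters any FACE-Q analysis, and the documents do not establish that. It does not remove the point, because the endpoint notes in Protocol 7.2.1.2 and SAP 5.1.2 are unqualified. If hidden text does use CTL, those notes conflict with it.

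Second, a reader might infer that control data at C1-a are already in hand and simply left out. That is not shown. Protocol 8.2 speaks of all Week 8 effectiveness assessments, but Protocol 8.1 limits this to the applicable ones, and the schedule of events is not visible.

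Third, a reader might infer that the plan will declare a spurious FACE-Q improvement. SAP 6.4.3 places all four tests on the primary endpoint. No FACE-Q test or success rule is shown, and the shared shifts used above have no source in the documents. Regression to the mean may also be modest, since visible entry selection is on evaluator-rated MIHAS and not on FACE-Q.

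Fourth, superiority to control is tested on MIHAS by a blinded evaluator, and nothing requires each secondary endpoint to show it again. That is correct, and it is why the point concerns interpretation only.

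Last, a control comparison does not cure everything. Subjects know whether they were injected, so expectation bias in a self-reported score remains.

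**Conclusion.** The point holds in limited form. Under the visible definitions and default rules, FACE-Q Satisfaction with Eyes, both scores and changes, is an uncontrolled before-and-after summary in TN, TC and TRT. As such it cannot support a statement of superiority to untreated control. Type I error and the primary conclusion are unaffected.

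A TRT minus CTL estimate would remove change common to both arms, but it is not precise. At the planned evaluable size it is informative for differences of roughly 0.5 to 0.6 SD and above; 73% power at 0.5 SD does not reach the 90% that the plan sets for its primary tests. These figures assume SD units of change, a normal approximation, and no precision gain from baseline adjustment. The conclusion also depends on what the withheld FACE-Q paragraph says, and the remedy depends on whether controls complete FACE-Q at C1-a.

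**What to change.** First, confirm from the schedule of events that controls have FACE-Q Satisfaction with Eyes recorded at baseline and again at C1-a before injection.

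If they do:
- Exempt this endpoint from the treated-only wording in SAP 5.1.2 and 6.1.2 and Protocol 7.2.1.2 and 13.4.1.2. This also reconciles those sections with the Week 8 definition in SAP section 6.
- Add a supportive TRT (V3) minus CTL (C1-a) difference in change from baseline, with a two-sided 95% CI from an ANCOVA on baseline score and (pooled) site, outside the hierarchy. SAP 6.4.5 confines site pooling to the imputation and logistic models, so it needs a line to cover this one.
- Keep the within-arm summaries as descriptive, and leave GAIS treated-only.
- State the limits beside the estimate: unblinded subjects, later assessment after touch-up, and the expected CI width.

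If they do not, state in the SAP and the report that the FACE-Q result is uncontrolled and does not address superiority to untreated control.

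The cost is wording in two documents and one table, with no new subjects or visits if the C1-a data exist. The reported effect will be less precise, and may be smaller, than the within-arm change.

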6.2 Safety Endpoints

All safety endpoints will be summarized for observed values in the SP by treatment group (TRT and DTRT) and overall (TOTT) and by injection technique (needle/cannula) (groups TN, DTN and NED as well as TC, DTC and CAN), if not otherwise stated. Analyses by treatment cycle will be based on the subset of subjects in the SP with treatment in the respective cycle.

6.2.1 Adverse Events

All AEs will be coded according to the Medical Dictionary for Regulatory Activities (MedDRA) version in effect at the time the database is locked.

In the electronic case report form (eCRF), AEs will be reported with their onset and information on study discontinuation (tick box "AE leading to Discontinuation of the Study" = "Yes") and treatment discontinuation (tick box "Action taken with Medical Device" = "Treatment suspended"). The start date of the AE will be the date of the record reporting the onset of the AE and the stop date will be the stop date or ongoing, if not yet resolved. For seriousness, intensity, causal relationship, and outcome the worst attributes of each AE will be documented. The worst outcome is defined in the following order (from best to worst):

- recovered/resolved
- recovered/resolved with sequelae
- recovering/resolving
- not recovered/not resolved
- unknown
- fatal.

TEAEs are defined as AEs with onset at or after the first administration of study treatment. The handling of missing start and stop dates are described in TEAEs will be assigned to a treatment cycle (see treatment cycles in Section 6) based on the following rules:

- For subjects of treatment groups TN or TC (and TRT), TEAEs will be grouped into two treatment cycles according to the AE onset date, as follows:
 - For subjects without retreatment:

An AE is considered treatment emergent for Cycle 1 if the start date of the AE is on or after the date of the initial treatment injection.

o For subjects with retreatment:

An AE is considered treatment emergent for Cycle 1 if the start date of the AE is on or after the date of the initial injection and before the date of retreatment.

An AE is considered treatment emergent for Cycle 2 if the start date of AE is on or after the date of the retreatment. In case of any doubts because of exact day or time of onset information missing, an AE will be rather be assigned to Cycle 2 than to Cycle 1.

• For subjects of groups DTN or DTC (and DTRT), an AE is considered treatment emergent for **Cycle 1** if the start date is on or after the date of delayed treatment at Week 8.

All other AEs are considered to be non-TEAEs (i.e., all AEs with start date prior to initial injection).

For TEAEs, an overall summary table will be provided, displaying the following content by treatment cycle and overall:

- Any TEAEs;
- Any related TEAEs;
- Any TESAEs;
- Any related TESAEs;
- Any TEAEs leading to discontinuation from study;
- Any related TEAEs leading to discontinuation from study;
- Any TEAEs leading to discontinuation of study treatment;
- Any related TEAEs leading to discontinuation of study treatment;
- Any fatal TEAEs and
- Any fatal TEAEs related to treatment.

For TEAEs, related TEAEs, TESAEs, non-serious TEAEs, TEAEs leading to discontinuation from study and related TESAEs, number of subjects with TEAEs and number of TEAEs will be summarized by SOC and PT for each treatment cycle and overall. TESAEs, TEAEs leading to discontinuation from study and related TESAEs will only be summarized if more than 5 subjects (over all treatment groups) experienced such a TEAE.

In addition, the following TEAE incidences will be shown overall and by treatment cycle:

- Number of subjects with TEAEs by PT;
- Number of subjects with TEAEs by worst intensity, by SOC and PT;
- Number of subjects with TEAEs by worst causal relationship, by SOC and PT;
- Number of subjects with TEAEs by worst outcome, by SOC and PT; and
- Number of subjects with TEAEs by maximum duration, by SOC and PT (duration categories: 1 to 3 days, 4 to 7 days, 8 to 14 days, 15 to 28 days, and > 28 days);
- Number of subjects with related TEAEs by worst intensity;

Number of subjects with related TEAEs by maximum duration (duration categories: 1 to 3 days, 4 to 7 days, 8 to 14 days, 15 to 28 days, and > 28 days);

Moreover, a summary of all related TEAEs will be provided, summarizing the number of events by severity and by duration.

The duration of TEAEs will be calculated by the difference of start and stop date plus 1 day. Missing start and stop days will be imputed as described in **ECLEPHICAL** If a TEAE is ongoing at study end, TEAE duration will be calculated as the difference between TEAE start date and last contact date + 1.

Moreover, the TEAE overview tables as well as incidences and number of related TEAEs (by PT and SOC) will be provided for the following subgroups, overall and by treatment cycle:

[figure not shown]
- Baseline MIHAS (2 vs. 3);
- Race (white vs. other);
- Ethnicity (Hispanic or Latino vs. not Hispanic or Latino);
- Age (< 45 years vs. ≥ 45 years);
- Touch-up (yes/no) (applies to Cycle 1 only);
- Sex; and
- Fitzpatrick skin type (I, II, III vs. IV, V, VI).

[figure not shown]
For all randomized subjects, a summary table presenting the number and percentage of subjects who experienced any AE at any time during study and the number and percentage of subjects with any non-TEAEs will be displayed by randomized treatment groups (TRT, CDTRT) and overall. This analysis will use subjects as randomized and will be based on all randomized subjects.

Additionally, AEs reported for subjects in the CTL group from date of randomization until Week 8 (pre-injection) will be summarized separately showing number of subjects with AEs and number of AEs by system organ class (SOC) and preferred term (PT). For subjects who received treatment at Week 8, AEs that started on the day of injection will not be considered in this analysis. For subjects who never received treatment, all AEs until end of study will be considered.

Listings for related TEAEs, TEAEs leading to study discontinuation, serious TEAEs, and serious TEAEs leading to death will be provided in the corresponding table section. For related TEAEs, AEs with delayed onset will be flagged. A delayed onset AE is defined as an AE with an onset more than 28 days after the most recent injection (i.e., the latest injection prior to the AE onset).

All AEs including non-TEAEs, as well as all reported device deficiencies, will be listed with all details recorded in the listings section.

Disposition of subjects

The number of subjects screened will be provided. Other subject disposition information (i.e., number of subjects randomized, treated and re-treated, as well as the number of subjects in each analysis population) will be summarized by treatment group and overall (TRT, CDTRT and TOTT) and additionally by treatment group and injection technique (needle/cannula) and overall (TN, TC, CDTN, CDTC, and TOTT). Similar descriptive analyses will be performed by site in a separate table.

The absolute and relative frequencies for subject's main reason for premature study discontinuation will be tabulated overall and separately for discontinuations before/at Week 8 and after Week 8 for various treatment groups (TN, TC, TRT, CDTN, CDTC, CDTRT and TOTT), based on all randomized subjects.

The time in weeks from randomization until premature discontinuation from study up to Week 8 will be displayed using a Kaplan-Meier curve. This curve will be provided for subjects in TRT and CTL groups based on all subjects randomized. Subjects who do not discontinue the study within the specified time window will be presented as censored at the date of their Week 8 visit. Subjects in TRT group that missed their Week 8 visit but did not discontinue will be censored at the target day of the Week 8 visit (i.e. Day 57 after last injection in treatment Cycle 1). For subjects who attended only visits up to Week 8 with date of last contact after Week 8, the date of discontinuation will be set to the date of the Week 8 visit.

The time in months from first treatment until premature discontinuation from study will be described by a second Kaplan-Meier curve for the TRT and DTRT groups in SP. Subjects who complete the study will be presented as censored at end of study.

Visit attendance (subjects expected at visit, subjects with visit performed on-site, subjects with visit performed virtually, subjects with missed visit due to COVID-19 pandemic or other reasons, subjects discontinued) will be presented in a frequency table for various treatment groups (i.e., TN, TC, TRT, CDTN, CDTC, CDTRT) based on all randomized subjects.

For 'Study discontinued', the cumulative number of subjects who discontinued the study before the respective visit will be displayed. For 'Subjects expected at visit', the following visits are defined as expected for all randomized subjects: Screening visit, initial treatment visit V1-a, V1-b, V2-a, V3 – V7-a, V8, V9 for TRT subjects; and Screening visit, visits C1-a, C1-b, C2-a, C3 and all following visits for CDTRT subjects, as defined in the visit schedules in the CSP column for TRT subjects and column for CDTRT subjects). Visits V2-b/C2-b and V2-c/C2-c are

only expected for subjects receiving an optional touch-up at visit V2-a/C2-a. In case of retreatment at visit V7-a for TRT subjects, follow-up visits V7-b and V7-c are also expected. For subjects who discontinue the study, the end of study visit V9/C7 is expected. Visits after premature discontinuation are generally not expected. The number of 'Subjects expected at visit' is thus calculated as number of randomized subjects – the number of subjects discontinued before the respective visit.

Percentages of 'Visit performed' (total) will be calculated relative to the number of subjects expected at the respective visit.

For columns relating to 'Subjects expected at visit', 'Study discontinued', 'Visit performed' (regularly on-site, virtually due to Coronavirus disease 2019 (COVID-19) pandemic) and 'Visit not performed' (total, due to COVID-19 pandemic, due to other reasons), only absolute numbers will be displayed. All performed and all not performed visits until regular study completion or premature discontinuation (as applicable for the respective subject) will be listed. Flags will also be included for visits performed virtually, visits not performed due to COVID-19 pandemic and visits not performed due to other reasons.

Protocol Deviation

The absolute and relative frequencies of major protocol deviations and other reasons for exclusion from the PP population will be tabulated, based on all randomized subjects for groups TN, TC, TRT, CTL and overall.

Additionally, major protocol deviations and other reasons for exclusion from the PP population related to COVID-19 pandemic will be presented in a separate table. For this purpose, each protocol deviation will be categorized whether it was related to the COVID-19 pandemic or not.

Minor protocol deviations will be listed only.

A listing of all documented impacts of COVID-19 pandemic on study conduct (incl. disruptions and modifications not constituting protocol deviations) will be provided. This listing will present investigational site identifier, randomized treatment group and information on impact of COVID-19 pandemic for all randomized subjects. In case the study conduct was impacted by COVID-19 pandemic, classified disruption or modification (e.g. visit performed virtually, time schedule deviation) and details on disruption or modification will be presented.

Demographic data and baseline characteristics

Demographic data (age, age category, sex, ethnicity, race and Fitzpatrick skin type) as well as weight, height and BMI and MIHAS baseline score as assessed by the blinded evaluator will be summarized by various treatment groups (i.e., TN, TC, TRT, CDTN, CDTC, CDTRT) and overall for the ITT, SP, PP populations and for all randomized subjects. Fitzpatrick skin type will additionally be categorized into type I-III and type IV-VI. Age will additionally be presented in categories of "< 45 years" and " \geq 45 years".

Previous and concomitant medication and non-drug treatment

Previous and concomitant medication will be coded by use of the World Health Organization Drug Dictionary (WHO-DD) whereby the version in effect at the time the database is closed will be used for analysis.

Rules for separation of previous and concomitant medication are given in concomitant medication are gi

Frequencies of previous and concomitant treatments will be given based on Anatomical Therapeutic Chemical (ATC) Classification System code levels 2 and 3 for the SP by treatment

groups TN, TC, TRT, CDTN, CDTC, CDTRT, and overall. Indications for concomitant therapies will not be coded and will only be listed.

Non-drug treatments will be coded using the MedDRA version which is in effect at the time the database is closed. Non-drug treatments will be displayed by SOC and PT levels for the SP by groups TN, TC, TRT, CDTN, CDTC, CDTRT, and overall.

Medical history and concomitant diseases

Medical history and concomitant diseases will be coded using the MedDRA dictionary and reported by SOC and PT levels for the SP by groups TN, TC, TRT, CDTN, CDTC, CDTRT and overall.

Rules for separation of medical history and concomitant diseases for missing or incomplete dates are given in complete also accounting for missing or incomplete stop dates.

Extent of exposure

Frequencies of subjects receiving initial treatment, touch-up and retreatment, if applicable, will be summarized by various groups (i.e., TN, TC, TRT, DTN, DTC, DTRT, NED, CAN, and TOTT) for SP.

Data on injection volume, technique, number of injection points, injection plane, and if ice was used (pre- and post-injection) will be analyzed for each treatment of the right IOH and left IOH separately. Injection volume will also be summarized for both IOHs combined. Number of injection points will be presented via summary statistics and also as frequencies using categories of 1, 2, 3, 4-9 and 10-18 injection points. These analyses will be displayed by various groups (i.e., TN, TC, TRT, DTN, DTC, DTRT, NED, CAN, and TOTT) for SP.

Further, injection-technique information (cannula/needle) will be summarized for TRT, DTRT and TOTT groups based on SP for each treatment of the right IOH and left IOH separately.

Additionally, frequencies of reasons for performed and not performed touch-up and retreatment will be summarized by treatment groups TN, TC and TRT for SP.

Listings on extend of exposure will be presented based on all subjects treated.

